#### 6.6 Sample size

A total size of 24 subjects is estimated, divided into 2 intervention groups. (12 subjects per group)

#### 6.6.1 Calculation of the sample size

Although there are no references on the calculation of the sample size in phase I studies, it was considered pertinent to perform it according to the presentation of adverse events referred by Christ T, in a randomized controlled trial of parallel groups, single blind, with randomization where

it was evaluated the efficacy and tolerance of a 5% dexpanthenol ophthalmic gel versus a 5% panthenol ointment in 48 subjects with corneal erosion, keratoconjunctivitis by UV radiation or similar conditions. The intervention consisted in the application of 1 cm of the gel and the ointment during 4 and 3 days, respectively. [20]

The percentage of good tolerance that was presented with the gel was 25%, so it is expected that no more than 10% of the subjects report a bad tolerance with the formulation proposed in this protocol.

The sample size was calculated using the formula for proportions

$$n = p (1 - p) \left( \frac{Z_{1-\alpha + Z_{1-\beta}}}{p - p0 - \delta} \right)^2$$

With a statistical confidence of 95% corresponding to the type I error, equal to 1.96, with a power of 80%, corresponding to the type II error, equal 0.84.

According to the previous calculation, the result is 19 subjects, which was increased by 20% for the probable losses. The total sample size required is 24 subjects. Therefore, each group will consist of 12 subjects, who will provide an eye for analysis.

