In the evaluation of day 3, 50 vs 45% of the subjects, of the group with gel and ointment, presented corneal erosions less than 10% with reference to the basal size, respectively. At the final visit, all the erosions were less than 10% of the size, in both groups, with a tendency to be faster in the decrease in size in the gel group. Regarding the symptoms, they were reported non-existent in both groups during the final evaluation. Tolerance was reported as very good by the patients. However, in the group with ointment there was a higher incidence of alterations in vision, compared with the gel group. [20]

In 1996, Martin Göbbels and Dorothea Groβ, published the results of a double-blind, controlled, randomized clinical trial conducted in 50 subjects with dry eye, divided into two groups, which were administered five drops per day of tears artificial with and without dexpanthenol for 6 weeks. The outcome variables were measured before and after the intervention. Corneal permeability was evaluated by means of fluorophotometry and the Schirmer test. In addition, staining with Bengal rose and lacrimal rupture time was performed. All subjects made a subjective evaluation of complaints (tolerability).

Version: 1.0

After 6 weeks of intervention, the epithelial permeability of the cornea was better, in the group with dexpanthenol, compared to the other group. The other parameters did not show differences. [21]

In another double blind, randomized clinical trial, the efficacy of a dexpanthenol plus vitamin A ointment and a gel based on a hemodialysis free of calf blood proteins was evaluated and compared. We included 54 subjects with superficial corneal lesions due to foreign metallic bodies. After the removal of the foreign body and the debris, an exploration of the anterior segment with a slit lamp was performed. The depth of the corneal lesion was classified (superficial, medium and deep) and the percentage of damaged area was calculated by planimetry. The intervention consisted in the application, single dose, of the gel with dexpanthenol + vitamin A or the hemodialysis in the conjunctival cul-de-sac. Subsequently, the eye was bandaged. The control review was performed 24 hours later and, if necessary, during the following days. Healing was defined as a reduction of the initial corneal injury in less than 5% of the total.

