#### - Contact lens users.

#### 6.2.2.2 Medical and therapeutic criteria

#### 6.2.3 Elimination criteria

- Withdrawal of the consent letter under information.
- Presentation of a serious adverse event.
- No tolerability or hypersensitivity to any of the compounds used during the tests (fluorescein, green lysine, tetracaine)
- No tolerability or hypersensitivity to any of the investigational drugs.
- Adherence <50% determined by the diary of the subject.

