#### 6.4.1.2 Primary outcome variables of tolerability

- Burning
- Foreign body sensation
- Itching
- Eye comfort index

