#### 8.3 Statistical methodology

#### 8.3.1 Analysis of primary and secondary outcome variables

The statistical analysis will be carried out by personnel of Sophia Laboratories. The statistical program SPSS version 19 (IBM Corporation, Armonk, NY, USA) will be used.

The designated personnel will be blinded to the intervention groups. The coding will be done using consecutive numbers for each intervention group.

The data will be collected and sorted in an excel sheet. Later they will be exported to the platform of the SPSS program. The variables will be categorized according to their nature.

The result of the continuous quantitative variables will be presented in measures of central tendency: mean, standard deviation and ranges. See Table 4. Scales to be used

The normal distribution of the results will be obtained by the Kolmogorov-Smirnov test.

The statistical analysis of the continuous **quantitative variables** to find significant differences (p) will be the following:

- Intra-group analysis: Wilcoxon rank test.
- Inter-group analysis: Mann-Whitney U test.

The level of difference to consider significance will be an alpha of 0.05 or less.

The result of nominal and ordinal qualitative variables will be presented in frequencies, proportions and percentages.

The statistical analysis to identify significant differences of the **qualitative variables** will be done creating 2x2 contingency tables and it will be carried out in the following way:

- Intra-group difference: McNemar or Pearson test.
- Difference between groups: test χ2 (Chi-square) of Pearson.

The level of difference to consider significance will be an alpha of 0.05 or less.

For the reporting of adverse events all eyes of those participants who were randomly assigned to an intervention group after the baseline visit will be considered. The results will be expressed in number of cases (eyes).

The final report of the results will be shown in tables or graphs, as appropriate.

It will be considered that the investigational drug is safe and tolerable when there are no clinical and statistical differences in all the variables of primary outcome, with respect to its comparator.

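### The 80% power in section 6.6.1 belongs to a bad-tolerance proportion that is never defined or analysed, and removals for intolerance can leave the tolerability comparisons

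*Combined protocol and SAP*

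**What the plan says.** Section 6.6.1 takes its reference figure from a cited randomised trial of a dexpanthenol gel against an ointment: "The percentage of good tolerance that was presented with the gel was 25"%. The sentence continues: "so it is expected that no more than 10% of the subjects report a bad tolerance with the formulation proposed in this protocol". The error rates follow: "With a statistical confidence of 95% corresponding to the type I error, equal to 1.96", and "with a power of 80%, corresponding to the type II error, equal 0.84". A formula for proportions is said to give 19 subjects, raised by 20% for losses to 24, or 12 per group.

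Tolerance appears in two other forms:

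- Section 6.2.3 removes a subject for "No tolerability or hypersensitivity to any of the investigational drugs". It gives no threshold and no link to an outcome.
- Section 6.4.1.2 lists four primary tolerability variables: burning, foreign body sensation, itching and "Eye comfort index". Section 6.4.3.9 scores the symptoms 0 to 4 for severity and for frequency, with no cut that marks a failure.

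Section 8.3.1 calls the product safe and tolerable when "there are no clinical and statistical differences in all the variables of primary outcome, with respect to its comparator". Section 6.4.1.1 adds three primary safety variables: goblet cell density, epithelial defects and adverse events. Section 8.3.1 reports adverse events for all randomised participants, but admits to the statistical analysis only subjects with adherence above 60%. Section 8.3.3 limits the intention-to-treat set to subjects who completed the baseline visit and Visit 1.

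**The concern.** A power statement means something only for a quantity that the trial measures and tests. Here that quantity is a proportion with bad tolerance. It is absent from the outcome lists in 6.4.1, from Table 4 and from the analyses in 8.3. A reader of 6.6.1 would believe that a tolerance comparison has 80% power, but the plan contains no such comparison.

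The second issue is what happens to a subject who cannot tolerate the gel. Removal under 6.2.3 is the plainest tolerability failure the protocol recognises, yet it is not itself an outcome. The removed subject may also supply no data to the four variables that stand for tolerability. The product could then be declared tolerable on the subjects who tolerated it, without the number removed for intolerance being set against the comparator.

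**Working it through.** **1. The plan's own figure.** The formula in 6.6.1 is n = p(1 − p)[(Z₁₋α + Z₁₋β)/(p − p₀ − δ)]², with Z values 1.96 and 0.84, which sum to 2.80. No δ is given, and p and p₀ are not matched to 10% and 25%.

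- p = 0.10, p₀ = 0.25, δ = 0: 0.09 × (2.80/0.15)² = 31.4, so 32.
- p = 0.25, p₀ = 0.10, δ = 0: 0.1875 × (2.80/0.15)² = 65.3, so 66.
- With p = 0.10 and p₀ = 0.25, 19 appears if δ is about 0.043: 0.09 × (2.80/0.193)² = 18.9.

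So 19 can be neither confirmed nor refuted. The last step does reproduce: 19/0.8 = 23.75, so 24. The formula has a single p(1 − p) term, which makes it a one-group size, yet the result is split over two groups.

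**2. From 25% to 10%.** The first figure is a share with good tolerance. The share with bad tolerance depends on how the other 75% were classed, and 6.6.1 does not say. No bad-tolerance rate follows.

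**3. Does the stated power fit any planned test?** Suppose, as an assumption the text does not make, that 25% is a reference rate of bad tolerance and the arms are compared at 10% v 25% with the Pearson test of 8.3.1. Power at 12 per arm is 12.4% by exact enumeration (15.6% by normal approximation), and 80% power needs 100 per arm. The 80% therefore does not describe that comparison either.

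**4. What 12 per arm can say.** With no failures, the exact upper bound is 1 − a^(1/n), where a is the tail probability.

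- 0/12, one-sided 95%: 1 − 0.05^(1/12) = 22.1%.
- 0/12, two-sided 95%: 1 − 0.025^(1/12) = 26.5%.
- 1/12: the two-sided 95% interval (Clopper-Pearson) is 0.2% to 38.5%.

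**5. Where a removed subject goes.**

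| Variable | When measured | Effect of removal for intolerance |
|---|---|---|
| Eye comfort index | Baseline and final visit in the 6.5 schedule (6.4.4 also lists screening) | No post-treatment value if the final visit is not made |
| Burning, foreign body sensation, itching | Also at Visit 1, day 3 ± 1 | Excluded by 8.3.3 if removed before Visit 1; kept in that set if removed later |
| Any analysed variable | Adherence above 60% | May be excluded, depending on the denominator |
| Adverse events | All randomised | Counted only if recorded as an adverse event |

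On the third row, four applications a day for 10 days make 40. Three full days give 12/40 = 30%, below the filter. If adherence is instead averaged over the visits actually made, the same subject could pass. The protocol does not settle this for a removed subject.

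**6. Illustration, not a prediction.** Take 4/12 removals on PRO-167 and 0/12 on the comparator. Pearson χ² = 24 × (4 × 12 − 0 × 8)²/(12 × 12 × 4 × 20) = 4.8, p = 0.028. For 3/12 v 0/12, χ² = 24 × 36²/(12 × 12 × 3 × 21) = 3.43, p = 0.064. If the four were removed before Visit 1, the tolerability variables would be compared in 8 v 12.

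**The case against.** A reader might infer that poor tolerance never enters the conclusion, or that the decision rests on the four tolerability variables alone. The documents do not support this. The rule in 8.3.1 covers all seven primary variables, and one of them, adverse events, is counted over all randomised participants. Section 6.6.1 itself ties the sizing to adverse events in the cited trial. Section 9.3.1.3 describes adverse events broadly, 9.3.1.1 asks for withdrawal of the product to be recorded, and 8.1.1 asks about adverse events and the reason for leaving when a subject cannot be rebooked. Most intolerance serious enough for removal would probably be captured. In the 4 v 0 illustration, if those removals were recorded as adverse events and there were no others, the adverse-event comparison would give the same p = 0.028.

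A reader might also infer that the trial set out to show a rate of 10% or less and is too small to do so. It is true that no result in 12 subjects could bound the rate at 10%. But 10% is stated as an expectation, the hypothesis is similarity to the comparator, and the study is an exploratory phase I trial.

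Nor does the Background statement "Tolerance was reported as very good by the patients" prove a contradiction with 25% good tolerance. The two could be categories of one scale.

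What survives is narrower. No text requires a removal for intolerance to be recorded as an adverse event, and 6.2.3 lists intolerance separately from serious adverse events. Adverse events are also a mixed count of any event, which is not a tolerance rate. And a planning expectation that carries a power claim should refer to something the trial analyses.

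**Conclusion.** The concern holds in this limited form. The stated 80% power is attached to a proportion that is inferred from an unrelated figure, undefined, and compared nowhere, so it describes no planned analysis. Intolerance has a route into the decision through adverse events, but the protocol does not guarantee that a removal takes it, and such a subject can be missing from the tolerability comparisons.

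The honest statement of size is precision: with 0/12 failures in an arm, rates up to 22.1% (one-sided 95%) or 26.5% (two-sided 95%) remain compatible with the data. These bounds assume that all 12 randomised subjects per arm are counted, one eye each. How many subjects will be removed is unknown, so no bias can be quantified. This calls for a correction to the protocol and SAP text and does not by itself make the design unusable.

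**What to change.** Leave the removal rule as it stands and make two changes.

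1. **Sections 6.4.1.2 and 8.3.1.** Add, as a tolerability failure, the proportion of all randomised subjects removed under the existing intolerance or hypersensitivity criterion for the investigational drugs. Report it by arm with an exact 95% confidence interval. Removals for reactions to the test dyes or anaesthetic fall under a separate criterion and are not counted here. Add a symptom-severity component only if the sponsor fixes the cut before unblinding. Without it, the count needs no symptom data from subjects who leave for other reasons. Listing it in 6.4.1.2 brings an eighth variable under the decision rule, and 8.3.1 should say so. Because 3/12 v 0/12 would still be non-significant, the intervals should be shown beside any test.
2. **Section 6.6.1.** Delete the step from 25% good to 10% bad tolerance and the 80% power statement. Call 12 per arm pragmatic, and state that with no failures in an arm the exact upper bound is 22.1% (one-sided 95%) or 26.5% (two-sided 95%).

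The cost is protocol and SAP wording, one extra table, and a stated precision less favourable than the present power claim. No new visits, subjects or measurements are needed.

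### The 19 subjects cannot be derived from the stated inputs, and the 80% power of a one-sample formula does not carry over to the two-arm comparisons

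*Combined protocol and SAP*

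**What the plan says.** Section 6.6.1 takes its rates from a published trial of a dexpanthenol gel against an ointment: "The percentage of good tolerance that was presented with the gel was 25%, so it is expected that no more than 10" per cent of subjects will report bad tolerance with the new formulation. It prints the formula n = p(1 − p)[(Z for type I error + Z for type II error)/(p − p0 − delta)]². The constants are given as follows: "With a statistical confidence of 95% corresponding to the type I error, equal to 1.96, with a power of 80" per cent, with 0.84 for the type II error. The outcome is "According to the previous calculation, the result is 19 subjects, which was increased by 20% for the probable losses", giving 24. The section ends: "Therefore, each group will consist of 12 subjects, who will provide an eye for analysis". Section 6.6 repeats the split: "A total size of 24 subjects is estimated, divided into 2 intervention groups".

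Section 8.3.1 sets the between-group tests at alpha 0.05. For qualitative variables: "Difference between groups: test χ2 (Chi-square) of Pearson". For continuous variables, which include the primary variable goblet cell density: "Inter-group analysis: Mann-Whitney U test". The product is to be considered "safe and tolerable when there are no clinical and statistical differences in all the variables of primary outcome", relative to the comparator.

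**The concern.** There are three gaps between the calculation and its use.

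- **Inputs.** Delta appears in the formula but has no value anywhere in the document, and the text does not say which of 25% and 10% is p and which is p0. The 19 therefore cannot be checked.
- **Design.** The formula has one variance term and a fixed reference rate, so it sizes a single group. Its result is used as the total for two randomised arms. The 80% power that goes with it does not describe a comparison of 12 with 12.
- **Outcome.** The 25% is labelled good tolerance and the 10% bad tolerance, so the text does not show that both are rates of one outcome. This may be a translation slip, but it leaves the contrast undefined.

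The stake is how a null result will be read. Under 8.3.1 a non-significant test counts towards calling the product safe and tolerable. A reader who takes the 80% at face value would see such a result as fair evidence of similarity.

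**Working it through.** **Inputs from 6.6.1:** z = 1.96 and 0.84 (sum 2.80); rates 0.10 and 0.25; delta not stated; n = 19; losses 20%; 12 per group. **From 8.3.1:** Pearson chi-square and Mann-Whitney, alpha 0.05 (taken as two-sided).

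**1. The plan's 19, with delta = 0 (assumption)**

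- p = 0.10, p0 = 0.25: 0.09 × (2.80/0.15)² = 31.36, so 32.
- p = 0.25, p0 = 0.10: 0.1875 × (2.80/0.15)² = 65.33, so 66.

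Neither is 19.

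**2. What delta would give 19 with z = 1.96?** The result rounds up to 19 when the absolute value of p − p0 − delta lies between 2.80√(p(1 − p)/19) and 2.80√(p(1 − p)/18).

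- p = 0.10: 0.1927 to 0.1980, so delta is 0.043 to 0.048, or −0.348 to −0.343.
- p = 0.25: 0.2782 to 0.2858, so delta is −0.136 to −0.128, or 0.428 to 0.436.

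Round values of delta miss:

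| p, p0 | delta | n before rounding |
|---|---|---|
| 0.10, 0.25 | −0.05 | 70.56 |
| 0.10, 0.25 | 0.05 | 17.64 |
| 0.10, 0.25 | 0.10 | 11.29 |
| 0.25, 0.10 | −0.05 | 36.75 |
| 0.25, 0.10 | −0.10 | 23.52 |
| 0.25, 0.10 | −0.15 | 16.33 |

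**3. A route with another z.** With 1.645, p = 0.25, p0 = 0.10 and delta = −0.10: 0.1875 × (2.485/0.25)² = 18.53, so 19. The complement form (p = 0.75, p0 = 0.90, delta = +0.10) gives the same value. This contradicts the printed 1.96, although the formula's subscript reads 1 − alpha.

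**4. The loss step.** 19/(1 − 0.20) = 23.75, so 24. This step reproduces.

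**5. Two-arm power of the chi-square test** (exact enumeration, no continuity correction, two-sided 0.05). The documents do not define the contrast, so two readings are shown.

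| Reading (assumption) | 12 v 12 | 9 to 12 evaluable per arm |
|---|---|---|
| A: 10% v 25% of one outcome | 12.4% | 7% to 18% |
| B: literal, 25% good v 90% good | 95.8% | 87% to 96% |

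Reading B does not rescue the 19. With z = 1.96 and delta = 0 the formula then gives 0.09 × (2.80/0.65)² = 1.67, so 2, or 0.1875 × (2.80/0.65)² = 3.48, so 4.

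**6. Without using the 25%.** Against 10% in one arm, 12 per arm reaches 80% power only when the other arm is at about 61%. A true 10% v 40% is non-significant in 61% of trials.

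**7. Mann-Whitney.** The documents give no SD, so the shift is in SD units, assuming normal data with equal SD (200,000 simulated trials per setting, exact two-sided test). At 12 v 12, power is about 80% at a shift of 1.25 SD. With 10 and 9 evaluable, about 1.45 SD is needed.

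**8. Precision that 12 per group does give.** With 0 events in 12, the exact two-sided 95% upper limit is 1 − 0.025^(1/12) = 26.5%. With 0 in 10 it is 1 − 0.025^(1/10) = 30.8%.

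**The case against.** The strongest reply has four parts.

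- **Not derivable is not the same as wrong.** The 32 and 66 rest on delta = 0, which the protocol never states. A delta of 0.05 comes within about one subject (17.64), and z = 1.645 with an ordinary 10% margin gives 19. This stands: the 19 is not disproved. But no single set of values agrees with both the printed 1.96 and a round delta, and a reader cannot tell which route was used.
- **The protocol never says the 80% belongs to a between-group test.** Literally true; it is attached to the formula. But it is the only power quoted, it justifies the size of a two-arm trial, and the only arm comparisons planned are those in 8.3.1. Supplying delta would not change this.
- **The power figures depend on the reading.** They run from 12% to 96%, and the protocol does not say that 10% and 25% are arm rates. Agreed; both are labelled as assumptions. The spread itself shows that the stated 80% carries no definite meaning for the comparison.
- **The study is exploratory, its specific objectives are descriptive, and 8.3.1 also asks for no clinical difference.** This is why the size is not challenged. It does not support the quoted power, and 8.3.1 gives no threshold for a clinical difference.

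**Conclusion.** The point holds. As written, the 19 does not follow from the stated inputs: they give 32 or 66 at delta = 0, and reaching 19 needs either an undisclosed, non-round delta or a z value other than the one printed. Separately, and whatever delta was, a one-sample result has been divided between two arms, so the 80% is not shown for the chi-square or Mann-Whitney comparisons. Actual two-arm power is undefined by the documents. It is 12.4% at 12 per arm if 10% and 25% are the arm rates, and 95.8% on the literal good-tolerance reading, under which the formula with delta = 0 would ask for only 2 or 4 subjects. The step from 19 to 24 is sound, and 24 subjects is not in itself at fault for an exploratory phase I study.

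**What to change.** Keep 24 subjects. In 6.6.1, stop presenting the 80% as the power of the two-arm study, and do one of the following:

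- **(a)** State that 24 (12 per group) is not based on power for the between-group tests, and give the precision it delivers. For example: with 0 of 12 events in a group the two-sided 95% upper limit is 26.5%, or 30.8% with 10 evaluable.
- **(b)** State p, p0, delta, the z value and the sidedness, show that they give 19, and report the actual two-arm power for the assumed rates.

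In either case, reword the 25% and 10% so that both refer to one defined tolerance outcome.

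In 8.3.1, after the rule for calling the product safe and tolerable, add: *A non-significant between-group test with 12 subjects per group is not by itself evidence of similarity.*

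The cost is protocol wording in 6.6.1 and one sentence in 8.3.1. A stated figure becomes less favourable. No subjects, visits, procedures or analyses are added.
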